4.7.2. Risk window definitions

Not applicable.

4.7.3. Analyses for Effectiveness Endpoint Measures

Since this study was not designed as the efficacy study for different indications that contribute significant information about product safety, the analyses in the SAP are considered fit-for-purpose for an abbreviated clinical study report with data scope including 1) full safety data and 2) limited efficacy data to support the benefit-risk evaluation.

Given the reporting nature of the PROMIS items, the reported PRO response was sparse. Therefore, they were excluded from the planned CSR analyses.

The analyses for effectiveness endpoints are based on full analysis set (Section 4.2). The analyses for the abbreviated CSR focus on hematologic and renal function laboratory parameters and SCD-related clinical events.

Participant disposition, non-SCD medical history, concomitant medication, study drug administration (including dosage changes initiated by the participant and by the physician), demographics and baseline characteristics will be summarized descriptively based on full analysis set.

The descriptive statistics will be provided for the following medications:

- long-acting opioids
- Erythropoiesis-stimulating agents
- Other relevant pain meds (e.g. Gabapentin, Lyrica, Cymbalta)
- SCD disease modification agents (hydroxyurea, Adakveo/crizanlizumab, L-Glutamide/levoglutamide).

The study drug administration will be categorized as 1) < 1 month, 2) >=1, <2 months, 3) < 3 months, 4) >=3 months, < 6 months, 5) >=6 months, < 9 months, 6) >=9 months, < 12

months, 7) ≥ 12 months, < 18 months, 8) ≥ 18 months, < 24 months, 9) ≥ 24 months, < 36 months, 10) ≥ 36 months, < 48 months and 11) ≥ 48 months.

The following effectiveness endpoints will be summarized descriptively:

- Change from pre-Oxbryta treatment period in the following hematologic parameters corresponding to treatment with Oxbryta® (Voxelotol):
 - Hb
 - Hemolysis measures, including % reticulocytes, absolute reticulocytes, bilirubin (total, direct, and indirect)
 - ALT and AST

Analysis: Observed and change from pre-Oxbryta treatment period on Hb, Hemolysis measures will be summarized descriptively ([Section 4.7](#)) by visit

If a queried hemolysis value remained greater than its threshold listed in the table below, the value would be deemed erroneous and excluded from the analysis,

Parameter	Threshold
Reticulocyte Count (absolute)	10,000 $10^{9}/L$
Ferritin	100,000 $\mu g/L$

- Change from pre-Oxbryta treatment period in the following Chemistry parameters corresponding to treatment with Oxbryta® (Voxelotol):
 - Ferritin

Analysis: Observed and change from pre-Oxbryta treatment period on ferritin will be summarized descriptively ([Section 4.7](#)) by visit.

- Change from pre-Oxbryta® (Voxelotol) treatment period in renal function:
 - Creatinine (Serum)
 - Albuminuria (urine albumin/creatinine ratio [ACR])
 - Hemoglobinuria (urine dipstick positive for blood +1 or greater and ≤ 2 RBC by high power field)
 - Serum cystatin C
 - Estimated eGFR calculated using the CKD-EPI equation

Analysis: Observed and change from pre-Oxbryta treatment period on Creatinine (Serum), Albuminuria, Hemoglobinuria, Serum cystatin C and eGFR will be summarized descriptively ([Section 4.7](#)) by visit

- Rate of SCD complications including acute pain crisis, acute chest syndrome

(ACS), priapism, stroke, and transient ischemic attack (TIA), chronic or end stage kidney disease, iron overload, leg ulcers, cardiac malfunction, and pulmonary hypertension (PH) and RBC transfusions.

Analysis:

The number and percentage of participants with SCD complications including acute pain crisis, ACS, priapism, stroke, chronic or end stage kidney disease iron overload, leg ulcers, cardiac malfunction and PH and RBC transfusions will be summarized by SOC and PT throughout the treatment period.

The annualized incidence rate of SCD complications including acute pain crisis, ACS, priapism, stroke, chronic or end stage kidney disease iron overload, leg ulcers, cardiac malfunction and PH and RBC transfusions will be summarized by SOC and PT throughout the treatment period.

- **PGIC**

PGIC includes 7 response categories: Very much improved, much improved, minimally improved, no change, minimally worse, much worse and very much worse.

Analysis: The PGIC will be summarized as numbers and percentages by visit for each response category.

- **CGIC**

CGIC includes 7 response categories: Very much improved, much improved, minimally improved, no change, minimally worse, much worse and very much worse.

Analysis: The CGIC will be summarized as numbers and percentages by visit for each response category.

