Regardless of how long participants have been on Oxbryta® (Voxelotor) when they enroll in the study, participants will be followed for up to 5 years after their first dose of Oxbryta® (Voxelotor) treatment, or until they withdraw their consent to participate, or are discontinued from the study. Treatment, including interruptions and restarting treatment, will continue at the discretion of the treating physician, and there are no pre-defined treatment requirements. Participants may receive any additional medications prescribed by their treating physician or have any medical interventions that are deemed appropriate by the treating physician or study doctor. The participant or treating physician may discontinue Oxbryta® (Voxelotor) at any time. Participants who discontinue treatment with Oxbryta® (Voxelotor) earlier than 5 years will continue to be followed on study to collect clinical and health-related quality of life (HRQoL) outcomes for up to 5 years after their first dose of Oxbryta® (Voxelotor) treatment.

Participant safety and tolerability will be assessed throughout the study data collection period by the study doctor and reported to the Sponsor.

The overall study design is illustrated in [Figure 1](#).

Figure 1: Study Schema

SOC, standard of care.

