9.11.3. Effectiveness Endpoint Measures Analyses

Baseline Demographic Characteristics:

Baseline demographic characteristics will be summarized descriptively.

Endpoints:

- Change from pre-Oxbryta® (Voxelotor) treatment period in Hb, hemolysis measures, measures of iron overload, and renal function over time will be summarized descriptively.
- Annualized rate of significant SCD-related clinical events, for example VOC, ACS, priapism, stroke, TIA, chronic or end stage kidney disease, iron overload, leg ulcers, cardiac malfunction, and PH will be calculated. The association between change in Hbhemolysis marker and rates of SCD-related clinical events will be evaluated.
- Rates of outpatient visits (including infusion center, acute care, or telemedicine visit), ED visits, hospitalizations, acute and chronic RBC transfusions, home oxygen supplementation, and renal dialysis will be summarized with a similar approach as incidences of SCD-related clinical events. The total cost associated with clinical interventions will be summarized descriptively.

- HRQoL measures over time will be summarized descriptively. Proportions of participants with improved HRQoL measures will be calculated and the associated 95% Clopper Pearson Exact confidence intervals will be constructed as appropriate.
- Rates of SCD-related clinical events, healthcare resource utilization, total cost associated with clinical interventions (if available) and HRQoL while on Oxbryta® (Voxelotor) treatment will be compared with the corresponding measures prior to the first dose of Oxbryta® (Voxelotor) treatment, as appropriate.

Subgroup analysis:

Similar comparisons may be performed between the subgroup of participants who discontinue Oxbryta® (Voxelotor) treatment but remain in the study and those participants who remain on Oxbryta® (Voxelotor).

Other subgroup or sensitivity analyses may be performed.

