4. RESEARCH METHODS

4.1. Study design

This registry is an observational study designed to evaluate the effect of Oxbryta® (Voxelotor) in individuals with SCD. This registry is intended to benefit and support interests of participants, clinicians, regulatory bodies, payers, and industry by obtaining longitudinal data on Oxbryta® (Voxelotor). Approximately 500 participants with SCD who are prescribed and treated with Oxbryta® (Voxelotor) will be enrolled. The study will be conducted at approximately 35 sites in the US.

Any participant who is currently taking Oxbryta® (Voxelotor) or has been prescribed and will initiate treatment with Oxbryta® (Voxelotor), is eligible to participate. Eligible participants will receive treatment with Oxbryta® (Voxelotor) as prescribed by their physicians, as part of their usual care. Participants will be treated and evaluated per standard of care (SOC) and at the physician's discretion.

Participants will be introduced to the study by their health care team and will sign the informed consent form (ICF) or assent prior to any data collection for the study.

[figure not shown]
This study will collect data that are recorded in the participants' medical records and other secondary data sources such as Insurance and Pharmacy Claims. Study data will be collected at regular intervals (no more frequent than every 3 months) and entered in case report forms (CRFs) via an electronic data capture (EDC) system by the study staff.

Regardless of how long participants have been on Oxbryta® (Voxelotor) when they enroll in the study, participants will be followed for up to 5 years after their first dose of Oxbryta® (Voxelotor) treatment, or until they withdraw their consent to participate, or are discontinued from the study. Treatment, including interruptions and restarting treatment, will continue at the discretion of the treating physician, and there are no pre-defined treatment requirements. Participants may receive any additional medications prescribed by their treating physician or have any medical interventions that are deemed appropriate by the treating physician or study doctor. The participant or treating physician may discontinue Oxbryta® (Voxelotor) at any time. Participants who discontinue treatment with Oxbryta® (Voxelotor) earlier than 5 years will continue to be followed on study to collect clinical and health-related quality of life (HRQoL) outcomes for up to 5 years after their first dose of Oxbryta® (Voxelotor) treatment.

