4.3. Variables

Variable	Role	Data source(s)	Operational definition
Index date	Study period	Case report form	Inform consent date
Index year	Study period	Case report form	Inform consent date
Pre-Oxbryta	Study period	Case report form	Baseline: any assessments within 12 months before receiving first dose of Oxbryta® (Voxelotor)
Post-Oxbryta	Study period	Case report form	Follow-up period for up to 5 years after the first dose of Oxbryta® (Voxelotor)
End of Treatment	Study period	Case report form	Captured from end of treatment form
End of Study	Study period	Case report form	Captured from end of study form
Age	Demographics	Case report form	Age at first dose of Oxbryta
Sex	Demographics	Case report form	Captured from the inform consent and eligibility form
Race/Ethnicity	Demographics	Case report form	Captured from the inform consent and eligibility form

SCD genotype	SCD disease history	Case report form	Captured from SCD disease history form
Hydroxyurea use	SCD disease history	Case report form	Captured from SCD disease history form
Height	Baseline characteristics	Case report form	Captured from Physical examination form
Weight	Baseline characteristics	Case report form	Captured from Physical examination form
Pre-Oxbryta SCD complications	Medical history	Case report form	Captured from Pre-Oxbryta treatment form
Concomitant Medications	Concomitant Medications	Case report form	Captured from concomitant medications form
Hemoglobin	Effectiveness endpoint measures - Hematology	Case report form	Captured from laboratory assessment-Hematology form
Reticulocyte count (%)	Effectiveness endpoint measures - Hematology	Case report form	Captured from laboratory assessment-Hematology form
Reticulocyte count (absolute)	Effectiveness endpoint measures - Hematology	Case report form	Captured from laboratory assessment-Hematology form
White blood cells (WBC)	Effectiveness endpoint measures - Hematology	Case report form	Captured from laboratory assessment-Hematology form
Aspartate Aminotransferase (AST)	Effectiveness endpoint measures - Hematology	Case report form	Captured from laboratory assessment-Hematology form
Alanine Aminotransferase (ALT)	Effectiveness endpoint measures - Hematology	Case report form	Captured from laboratory assessment-Hematology form
Bilirubin (Total)	Effectiveness endpoint measures - Chemistry	Case report form	Captured from laboratory assessment-Chemistry form

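### The by-visit laboratory summaries set no condition on treatment status and the SAP's post-Oxbryta definitions disagree, so later visit means can mix on-drug and off-drug values

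*SAP*

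**What the plan says.** - **Endpoints.** SAP 4.7.3 words the hematology endpoint as "Change from pre-Oxbryta treatment period in the following hematologic parameters corresponding to treatment with Oxbryta® (Voxelotol)" and the ferritin endpoint as "Change from pre-Oxbryta treatment period in the following Chemistry parameters corresponding to treatment with Oxbryta® (Voxelotol)". The renal endpoint is worded "Change from pre-Oxbryta® (Voxelotol) treatment period in renal function", without the link to treatment.
- **Analysis.** For hematology, "Observed and change from pre-Oxbryta treatment period on Hb, Hemolysis measures will be summarized descriptively" by visit. The ferritin and renal sentences follow the same pattern. The effectiveness analyses use the full analysis set, and the titles of Tables 15.2.1 to 15.2.4 in SAP Appendix A add no treatment condition.
- **Follow-up.** Under SAP 4.1, participants who stop early "will continue to be followed on study to collect clinical and health-related quality of life (HRQoL) outcomes for up to 5 years", counted from first dose. Protocol 9.1.1.1 adds: "Treatment, including interruptions and restarting treatment, will continue at the discretion of the treating physician".
- **Post-Oxbryta period.** SAP 4.3 defines it as "Follow-up period for up to 5 years after the first dose of Oxbryta® (Voxelotor)". SAP 4.7.1 ends it at end of treatment or end of study, without saying which governs. SAP 4.7.4 (safety) runs it to end of study, and uses the date of pausing or discontinuation only if the end-of-study date is missing.
- **Other endpoints.** Protocol 9.11.3 says that event rates, resource use, cost and HRQoL "while on Oxbryta® (Voxelotor) treatment will be compared with the corresponding measures prior to the first dose". Its laboratory bullet has no such limit. SAP 4.7.3 names the treatment period for SCD complications, but not for laboratory values.

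**The concern.** SAP 4.7.3 centers the abbreviated report on hematologic and renal laboratory values and SCD-related events. Hb is the marker on which accelerated approval rested, and Protocol 7.1.2 describes the drug's binding as reversible. A mean Hb change that falls between early and late visits could therefore reflect loss of effect in people still taking the drug, or simply a growing share who have stopped or paused. As specified, Tables 15.2.1 to 15.2.4 would not let a reader separate the two. For hematology and ferritin, the display would also not match an endpoint expressly tied to treatment. Finally, two programmers working from the same SAP could choose different windows and produce different tables.

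**Working it through.** The plan states no figure on this point: about 500 participants chosen on feasibility, and no discontinuation rate, Hb effect or SD. The check is mainly textual, with an illustration at the end.

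**Step 1. Are off-drug samples in the database?** Yes, where they are taken as part of usual care. Stopped participants stay in follow-up (SAP 4.1; Protocol 10.4.1.2). The schedule in Protocol Appendix 1 collects clinical outcomes, including laboratory results, to month 60. Protocol 10.3.6.1.1 enters every available result from scheduled outpatient visits after treatment start.

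**Step 2. What would each definition admit to a by-visit mean?**

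| Definition | After stopping | During a pause |
|---|---|---|
| SAP 4.3: whole follow-up, up to 5 years | included | included |
| SAP 4.7.1, read as a cut at end of study | included | included |
| SAP 4.7.1, read as a cut at end of treatment | excluded if the stop date is usable | included |
| SAP 4.7.4: to end of study (safety) | included | included |

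In the third row, SAP 4.6 sets an end-of-treatment date that is missing, or known only to the year, to the end-of-study date. Such a participant's off-drug values stay in. No row yields a purely on-drug summary.

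**Step 3. Does other text settle which row applies?** No.
- SAP 4.7 invokes the 4.7.1 duration only for annualized rates.
- The Hb subgroup in SAP 4.2.1 takes the maximum increase over the study period. This points away from a cut at end of treatment but does not govern Tables 15.2.1 to 15.2.4.
- Protocol 9.11.3 allows an optional comparison of participants who stop with those who continue. It is not among the SAP subgroups in 4.2.1 or 4.7.5, so no planned table splits laboratory values by status.

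**Step 4. Illustration; every input is assumed.** Let f be the off-drug share of values at a visit, D the mean on-drug change, and r the fraction of D that persists off drug.

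Visit mean = (1 − f) × D + f × r × D

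With D = +1.0 g/dL:

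| f | r = 0 | r = 0.5 |
|---|---|---|
| 20% | 0.8 + 0 = 0.8 | 0.8 + 0.1 = 0.9 |
| 40% | 0.6 + 0 = 0.6 | 0.6 + 0.2 = 0.8 |
| 60% | 0.4 + 0 = 0.4 | 0.4 + 0.3 = 0.7 |

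To see growth over time, take a constant yearly stop rate a with no restarts: f at month 60 = 1 − (1 − a)^5. For a = 5%, 10%, 20% and 30%, f is 23%, 41%, 67% and 83%. With r = 0, the month-60 mean is 77%, 59%, 33% and 17% of the on-drug mean. With r = 0.5, it is 1 − f/2, or 89%, 80%, 66% and 58%. All of this supposes that stopped participants go on supplying laboratory values at the same rate as those on drug.

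**The case against.** The strongest reply is that pooling is inferred from silence. A reader might conclude that the SAP directs these values to be summarized whether or not the participant is on drug. No sentence says so. SAP 4.7.1 can be read as a cut at end of treatment, and the treatment-emergent definition in 4.7.4 gives end of treatment priority over end of study. On that reading, most post-stop values drop out. This stands: the defect is an unstated and inconsistent window, not an explicit pooling rule. It does not remove the problem, because pauses and imputed stop dates still let off-drug values in.

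A reader might also extend the conflict with endpoint wording to the renal measures. The renal endpoint carries no link to treatment, so there is no such conflict for Table 15.2.4. Nor do the documents support assuming that creatinine, cystatin C or ACR return toward baseline once the drug stops.

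It is also fair to say that the SAP does not depart from Protocol 9.11.3 on laboratory values, that describing everyone followed is legitimate for a registry gathering long-term data, and that an on-drug summary selects those who continue. These points argue for keeping the pooled display, not for leaving it alone. Tables 15.1.1 and 15.1.4 will show disposition and exposure duration, but cannot tell a reader which laboratory values at a visit were taken on drug.

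**Conclusion.** The point holds in a limited form. The laboratory window and the handling of pauses are not defined, the SAP's post-Oxbryta definitions disagree, and under every available reading some off-drug values can enter the by-visit means. For hematology and ferritin, this sits badly with endpoints tied to treatment; for renal measures, it is only a missing specification.

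For Hb, the tabled mean change would shrink at later visits without waning on drug if two conditions hold: the change is smaller off drug, and the off-drug share of sampled values rises with time. The size cannot be computed from the documents. The illustrative means, from 0.9 down to 0.4 g/dL against +1.0 on drug, show how much depends on the assumed inputs and are not estimates for this registry. The summaries are descriptive, so no test, error rate or power is affected. The harm is to interpretation, and the remedy is cheap enough that the change should be made.

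**What to change.** 1. In SAP 4.7.3, state the window for laboratory data, including how pauses and imputed end-of-treatment dates are handled, and reconcile 4.3, 4.7.1 and 4.7.4 with it.
2. Derive an on-drug or off-drug flag at each post-dose sample date from the End of Treatment and Physician Administration forms, plus participant-initiated interruptions where recorded. The Participant Adherence form in Protocol 9.4 is absent from the SAP 4.3 list, so the SAP should say whether it is available. If it is not, the SAP should say that such pauses may be missed.
3. Keep the pooled by-visit column in Tables 15.2.1 to 15.2.3 and add on-drug and off-drug columns, with n at each visit. Do the same in Table 15.2.4 as a supportive display.

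The cost is one derived variable and extra columns in four descriptive tables. The downsides are smaller numbers per column, and an on-drug column that describes those who continue; a footnote should say so, and the n at each visit makes the selection visible.

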9.12.2. Source Documents

- Source documents provide evidence for the existence of the participant and substantiate the integrity of the data collected. Source documents are filed at the study site.
- For this study, source data includes data recorded in the participant's medical records and other secondary data sources and collected as part of the participant's usual medical care.
- The study doctor must maintain accurate documentation (source data) that supports the information entered in the CRF.
- Study monitors will confirm that data entered into the CRF by authorized site personnel are accurate, complete, and verifiable from source documents.

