10.3.6. Effectiveness Data

10.3.6.1. Clinical Outcomes

10.3.6.1.1. Laboratory Assessments

The following data will be recorded on the CRF:

For pre-Oxbryta® (Voxelotor) Treatment Visits, only the most recent results from regularly scheduled outpatient visit will be entered.

For post-Oxbryta® (Voxelotor) Treatment Regularly Scheduled Outpatient Visits, all available results during the data collection period will be entered.

For post-Oxbryta® (Voxelotor) Acute Visits (Emergency Department, Hospitalization, Acute Pain/Infusion Center), only the results on the day of presentation (or first available results during the visit) and day of discharge will be entered, if available.

The following data from the most recent results will be recorded in the CRF:

- Hb (including % HbF at baseline and all follow up visits), white blood cells (WBC), absolute neutrophil count (ANC), mean corpuscular volume (MCV), mean corpuscular hemoglobin concentration (MCHC), Platelets, aspartate aminotransferase (AST), alanine aminotransferase (ALT), and lactate dehydrogenase (LDH).
- Hemolysis measures, including % reticulocytes, absolute reticulocytes, bilirubin (total, direct, and indirect)
- Measures of iron overload (ferritin, iron, TIBC, T2*MRI)
- Creatinine (Serum)
- Albuminuria (urine albumin/creatinine ratio [ACR])
- Hemoglobinuria (urine dipstick positive for blood +1 or greater and ≤ 2 RBC by high power field)
- Serum cystatin C
- eGFR calculated using CKD-EPI equation

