1. VERSION HISTORY AND LIST OF ABBREVIATIONS

Version history

Version/ Date	Associated Protocol Amendment	Rationale	Specific Changes
2/ 21-Nov-2024	Original Protocol 10 October 2023	Update to Section headers to provide clarity for the analysis and list of tables.	
Section 3.2: Updated SCD complications.
 
Section 4.2.1: Added subgroup in this section
 
Section 4.3: Modified age was based on the first dose of Oxbryta.
 
Section 4.6: Added imputation rule for the end of study and treatment dates
 
Section 4.7.1: Modified texts about post-Oxbryta
 
Section 4.7.3: Modified SCD-related events
 
Section 4.7.4:
 
 Removed the sentence of SCD related events Added an analysis period Added SAE listings Added 28 days to the TEAEs definition 
Section 4.7.5:
 
 Modified the title to subgroup analyses Added analysis for new added subgroup 
Appendices:
 
 Removed ‘Study Drug Administration and Dosage Changes Initiated by the Participant’ table Modified title for tables 15.2.5, 15.2.6, and 15.4 Added table 15.2.5.1 ‘Summary of Transfusions’ Added table 15.2.6.1 ‘Annualized Incidence Rate of Transfusions’ Updated table 15.3.3 title Added table 15.3.7 Added tables 15.5.1-15.5.4

3/ 24-Jan-2025	Original Protocol 10 October 2023	Update to Section headers to provide clarity for the analysis and list of tables.	Section 4.2: Modified analysis populations Section 4.7.3: Added texts to exclude lab values with the incorrect unit. Appendix 6.1: Modified the analysis population in the table title
-------------------	--	--	---

List of abbreviations

Abbreviation	Definition
ACR	albumin/creatinine ratio
ACS	acute chest syndrome
AE	adverse event
ALT	alanine aminotransferase
ANC	absolute neutrophil count
AST	aspartate aminotransferase
CGIC	Clinical Global Impression of Change
CRF	case report form
CKD-EPI	Chronic Kidney Disease Epidemiology Collaboration
CSR	Clinical Study Report
ED	emergency department
EDC	electronic data capture
eGFR	estimated glomerular filtration rate
ESA	erythropoietin-stimulating agent
FDA	(US) Food and Drug Administration
Hb	hemoglobin
HbF	fetal hemoglobin
HbS	sickle hemoglobin
HRQoL	health-related quality of life
ICF	Informed consent form
ICH	International Conference on Harmonization
ICU	intensive care unit
IRB	Institutional Review Board
LDH	lactate dehydrogenase
MCV	mean corpuscular volume

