4.7. Statistical methodology and analyses

The following general analysis will be followed for this study, unless otherwise specified.

Unless otherwise specified, continuous/quantitative variables will be summarized using descriptive statistics which will include the number of participants with data to be summarized (n), mean, standard deviation (SD), median, first and third quartile (Q1, Q3), minimum, maximum, and the number of missing observations. Minimum and maximum will be reported with the same number of decimal places as collected in raw data, while mean, median, Q1, Q3 will be reported with one extra decimal place, and SD will be reported with two extra decimal places. Descriptive statistics for categorical/qualitative variables will be presented with number of participants and percentage (%) of participants in each category.

Percentages will not include the missing category and will be calculated over the number of participants with available (non-missing) data. A category with a zero count will be presented as “0” and a category with a 100 percentage will be displayed as “100”.

The annualized incidence rate is defined as total numbers of a given event for all participants divided by the total patient-year where the total patient-year is defined as the sum of total duration (years) as defined in the Section 4.7.1 for all participants.

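### The SAP's only exclusion limit for absolute reticulocytes is an upper cut of 10,000 x 10^9/L, so implausible counts and low-side unit errors can stay in the by-visit summaries

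*SAP*

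**What the plan says.** SAP 4.7.3 lists the haemolysis endpoints as "Hemolysis measures, including % reticulocytes, absolute reticulocytes, bilirubin (total, direct, and indirect"), summarised as observed value and change from the pre-Oxbryta period by visit (Table 15.2.2 in Appendix A). It then gives one rule for erroneous values: if a haemolysis value that has been queried "remained greater than its threshold listed in the table below, the value would be deemed erroneous and excluded" from the analysis. The threshold table has two rows: absolute reticulocytes at 10,000 x 10^9/L and ferritin at 100,000 ug/L. There is no lower threshold, and % reticulocytes and bilirubin have no threshold at all.

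The version history gives the purpose of the version 3 change to this section: "Added texts to exclude lab values with the incorrect unit".

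SAP 4.7 sets the summary statistics, which include "mean, standard deviation (SD), median, first and third quartile (Q1, Q3), minimum, maximum". Neither document contains another exclusion rule for absolute reticulocytes. The protocol's general safeguard is source verification (9.12.2): "Study monitors will confirm that data entered into the CRF by authorized site personnel are accurate, complete, and verifiable from source documents".

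**The concern.** A rule meant to remove wrong-unit values should at least remove counts that cannot occur, and it should work in both directions. This one acts only on values that "remained greater than its threshold", and the threshold lies above the whole red cell count of a patient with sickle cell disease. Three kinds of error pass through it:

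- a value in the thousands, such as 500 entered as 5,000;
- a count entered in 10^12/L, such as 300 entered as 0.30, which is the mirror image of the cells/uL error that the rule does catch;
- a percentage entered in the absolute field.

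At stake are the by-visit mean, SD, minimum, maximum and change for one haemolysis measure in the abbreviated report. An implausible maximum or minimum could be printed, and the mean and SD could be distorted at visits with few results.

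**Working it through.** **Inputs.** The threshold comes from SAP 4.7.3. The blood values and the typical reticulocyte counts are assumptions, because the documents give none. The SAP does not say how the threshold was derived, so there is no figure of its own to reproduce.

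**1. Unit conversion.** 10,000 x 10^9/L = 10 x 10^12/L.

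**2. Total red cell count.** Haematocrit = RBC x MCV and Hb = haematocrit x MCHC, so RBC (10^12/L) = Hb x 1000 / (MCHC x MCV), with Hb and MCHC in g/dL and MCV in fL. At MCHC 33:

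| Assumed Hb, MCV | RBC (10^12/L) | Cut / RBC |
|---|---|---|
| 5 g/dL, 110 fL | 5000 / (33 x 110) = 1.38 | 7.2 |
| 12 g/dL, 60 fL | 12000 / (33 x 60) = 6.06 | 1.65 |
| 15 g/dL, 60 fL | 15000 / (33 x 60) = 7.58 | 1.32 |

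The first two rows bound the main assumption (about 1.6 to 7 times all red cells). The third shows that a higher Hb does not rescue the cut. Conversely, for the total count to reach 10 x 10^12/L, haematocrit would have to be 90% at MCV 90 fL, or 60% at MCV 60 fL.

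**3. Plausible absolute counts.** At 10% to 30% reticulocytes and RBC 2 to 4 x 10^12/L, the count is 200 to 1,200 x 10^9/L. The cut is 10,000/1,200 = 8 to 10,000/200 = 50 times these.

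**4. What the rule catches and misses**, for values not corrected at query:

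| True value (10^9/L) | Error | Entered | Result |
|---|---|---|---|
| 300 | cells/uL (x1,000) | 300,000 | excluded |
| 300 | x100 | 30,000 | excluded |
| 500 | x10 | 5,000 | kept |
| 600 | x10 | 6,000 | kept |
| 300 | in 10^12/L | 0.30 | kept |

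A cells/uL entry survives only if the true count is 10 x 10^9/L or less. A hundredfold error survives only if the true count is 100 or less.

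**5. Effect of one retained value on a visit mean**, assumed typical value 300:

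- 5,000 retained: (5,000 - 300)/100 = +47 at n=100; (5,000 - 300)/300 = +16 at n=300.
- 0.30 retained: (0.30 - 300)/100 = -3.0 at n=100; (0.30 - 300)/300 = -1.0 at n=300.

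**6. Effect on the SD**, if the other n-1 values have mean 250 and SD 120. SD^2 = [(n-2) x 120^2 + ((n-1)/n) x (5,000 - 250)^2] / (n-1). The SD becomes about 490 at n=100 and 323 at n=250.

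**The case against.** The rule is a backstop for values that have already been queried, not the whole of data cleaning. The protocol also has investigator sign-off on the CRF (9.9.1, 9.12.1) and monitor verification against source (9.12.2), and it refers to a completion guideline and a monitoring plan that are not part of these documents. For the high-side unit error the cut works: a typical count entered in cells/uL is removed, as are many hundredfold errors. The retained 5,000 in the illustration is a decimal slip, not a unit error on a typical count. The other haemolysis measures do not use this cut, the median and quartiles withstand isolated errors, and no decision rests on this mean in a descriptive report with limited efficacy data.

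Most of this stands, and it limits the size of the point. It does not remove it. The SAP does not say which values trigger a query. Protocol 9.13 lists limited monitoring and quality control as a limitation. The written rule would keep an impossible count even after a query had failed to resolve it.

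A reader might infer that impossible values are in the data, or that the rule tilts the endpoint towards benefit because a lower count looks like less haemolysis. The documents support neither. They show no retained error. A low-side error at follow-up looks like improvement, but the same error at baseline looks like worsening, so no net direction follows.

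**Conclusion.** The point holds as a minor one. The stated rule is one-sided, and its cut lies above any total red cell count plausible in this population. Implausible values in the thousands and counts entered in 10^12/L can therefore stay in the mean, SD, minimum, maximum and change by visit, unless a query or source check corrects them first.

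The red cell ceiling is a physiological assumption, not a figure from the documents. It is safe for sickle cell disease but not for every conceivable patient, since extreme microcytic polycythaemia (MCV 60 fL, haematocrit 60%) would reach the cut. The shifts in the mean and SD are illustrations under assumed typical values and visit sizes, not estimates of what has happened in this registry.

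**What to change.** Replace the single cut with a two-sided plausibility check, fixed before database lock.

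1. **Range.** Flag absolute reticulocytes below 5 or above 1,500 x 10^9/L. Both limits are assumptions for the sponsor to confirm. They trigger a review, not an automatic exclusion.
2. **Cross-check.** Where % reticulocytes comes from the same sample, compute the implied red cell count in 10^12/L as absolute count / (% / 100) / 1000. Flag it if it is implausible, or if it is more than 5-fold away from Hb x 1000 / (MCHC x MCV) when those are recorded. Example at Hb 8.5 g/dL, MCHC 34 g/dL and MCV 90 fL (RBC 2.78) with 10% reticulocytes: 300 implies 3.0 and passes; 5,000 implies 50 and 0.30 implies 0.003, and both are flagged.
3. **Missing inputs.** The range check must work alone. Assessments are entered only when done as standard of care (Protocol 9.7). MCV and MCHC are listed for the CRF (Protocol 10.3.6.1.1) but not in the SAP 4.3 variable table, so they would have to be added to the analysis data.
4. **Handling.** Query flagged values. Convert where the factor shows a clear unit error. Keep low counts that agree with % reticulocytes, for example in aplastic crisis, which Protocol 10.3.6.1.8 lists as a collected complication. Exclude only values that remain impossible.
5. **Symmetry and reporting.** Apply the same rule to pre- and post-Oxbryta values, and report the numbers converted and excluded per visit.

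The cost is SAP wording and a few lines of checking code on variables the protocol already lists. The downside is a few more queries and exclusions.
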